6.3 Statistical Methods

6.3.1 Analysis of Primary Outcomes of Interest

Propensity score analyses will be used to adjust for potential confounding by baseline covariates. First, bivariate analyses will be performed to evaluate relationships between each baseline covariate and neutropenia management strategy as well as each outcome of interest. Next, propensity scores will be derived from the predicted probabilities estimated from logistic regression models of the use of outpatient versus inpatient management during neutropenia conditional on all baseline factors determined to be true confounders (i.e., those associated with both exposure and outcome) and those determined to be potential confounders (i.e., those associated only with the outcome interests). Patients will then be stratified into five groups using quintiles of the estimated propensity score. The distributions of exposure within the quintiles will be examined for sufficient sample sizes and balance. Within each stratum, the patients managed as outpatient and those managed as inpatient will ideally have similar values of the propensity score and likewise the distribution of measured baseline covariates will be comparable between them.

PedsQL™ items will be reverse scored and linearly transformed to a scale of 0 to 100 such that higher scores will be reflective of better HRQOL. The PedsQL™ total score will be calculated as the sum of the item-specific scores divided by the number of answered items (33, 34).

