We will utilize linear mixed effect models to test the association between neutropenia management strategy and the PedsQL™ total score. Specifically, the two repeated measures of the PedsQL™ total score will be the outcome and regressed on time, group (outpatient versus inpatient) and interaction between time and group will be the fixed effects, and a subject level random effect will be included to account for the potential correlations between the repeated measures. Such mixed models are more powerful than ANCOVA or analysis of change scores, and they benefit from the added power arising from any correlation of repeated measures over time. A significant group by time interaction will suggest that the change of PedsQL™ is different between the two groups. Adjustment for differences in covariates across neutropenia management groups will be accomplished through the propensity score outlined above, and by controlling for confounding of any remaining unbalanced potential confounders. Secondary analyses will be performed for the cancer and fatigue modules as well as for the physical and psychosocial subscales of the PedsQL™.

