6.3.2 Analysis of Secondary Outcomes of Interest

Responses to each of the items on the PIP-D were summed to obtain a total score reflecting the amount of difficulty experienced when handling events faced by parents of children with serious illness. Higher scores indicate greater difficulty and increased pediatric parenting stress (31).

Responses to each of the items on the SDSC DIMS subscale are summed to get a total domain score that is mapped to a corresponding T-score using the SDSC scoring sheet. Higher T-scores are reflective of greater clinical severity of symptoms and a T-score greater than 70 is considered pathological (32). For the PCO, we will utilize appropriate standard statistical methods to evaluate the relationships with neutropenia management strategy

(outpatient versus inpatient). For binary outcomes, log-binomial regression with robust error estimates will be employed to obtain risk ratios (95% CI). For continuous outcomes, generalized linear models will be used incorporating the appropriate distribution based on a graphical assessment of the outcome data. All models will be adjusted for baseline propensity scores by quintiles. Log-binomial regression with robust error estimates will also be employed to obtain risk ratios (95% CI) comparing the incidence of any financial toxicity (versus none), separately for each item on the financial toxicity survey as well as overall across all survey items. For the total score obtained from the financial toxicity survey, we will utilize methods comparable to those described for the PedsQL™ total score in section 6.3.1 above.

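### Section 6.3.1 does not say how the propensity score enters the two-visit model; entered as ordinary covariates, it leaves the primary group-by-time estimate unadjusted

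*Combined protocol and SAP*

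**What the plan says.** Section 6.3.1 estimates a propensity score for outpatient management and then groups patients by it: "Patients will then be stratified into five groups using quintiles of the estimated propensity score". The PedsQL total score at the two visits is the outcome of a linear mixed model, "regressed on time, group (outpatient versus inpatient) and interaction between time and group will be the fixed effects". Each patient also has a random intercept, which allows for within-patient correlation. Inference rests on the interaction: "A significant group by time interaction will suggest that the change of PedsQL™ is different between the two groups".

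Confounding is handled in one further sentence: "Adjustment for differences in covariates across neutropenia management groups will be accomplished through the propensity score outlined above", and also "by controlling for confounding of any remaining unbalanced potential confounders". Neither part gives the form in which the score or the extra confounders enter the model.

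Section 6.3.2 says, after describing the models for the patient-centered outcomes, "All models will be adjusted for baseline propensity scores by quintiles". For the financial toxicity total score, which is measured at both visits, it says "we will utilize methods comparable to those described for the PedsQL™ total score in section 6.3.1 above".

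**The concern.** The primary estimate is a difference between groups in change over two visits. A covariate that enters without a time interaction adds the same amount to a patient's score at both visits, so it cannot alter that patient's change. Main-effect adjustment therefore corrects the group difference in level but not the group-by-time term on which the test is based.

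Stable differences in level are not the problem, because the change contrast already removes any factor that acts equally on both visits. What stays unadjusted is a baseline factor that influences both discharge strategy and the course of quality of life between visits.

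Section 6.2 acknowledges that the groups are not randomised and relies on analytic control of patient- and hospital-level factors. On the main-effect reading that control does nothing for the primary test. Two analysts following the same text could also report different primary estimates and p-values.

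**Working it through.** **1. The plan's own figures.** Section 6.4 gives 47 outpatients, 71 inpatients, SD 20, a significance level of 0.05, and detectable differences in mean change of 15.0 points (correlation 0) and 6.8 points (correlation 0.8).

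- SD of change = 20 × √(2(1 − ρ)), which is 28.28 at ρ = 0 and 12.65 at ρ = 0.8.
- √(1/47 + 1/71) = 0.188.
- Detectable difference at 80% power, normal approximation = (1.96 + 0.84) × SD of change × 0.188, which is 14.9 and 6.7.
- The F test with 1 and 116 degrees of freedom gives 15.03 and 6.72, with power 79.9% and 80.9% at the stated differences.

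The figures reproduce, and they confirm that the power calculation targets the unadjusted difference in mean change.

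**2. Algebra.** Let G be group, Q the quintile indicators and u the subject effect.

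- Visit 1: Y₁ = α + γG + δQ + u + e₁
- Visit 2: Y₂ = α + τ + (γ + θ)G + δQ + u + e₂
- Change: Y₂ − Y₁ = τ + θG + (e₂ − e₁)

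The term δQ drops out, so with complete pairs the estimate of θ is the raw difference in mean change. With quintile × time terms the change becomes τ + θG + λQ + (e₂ − e₁), and θ is adjusted.

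**3. Numerical confirmation, complete data.** Random-intercept REML fits to 20 simulated data sets gave group-by-time estimates that differed by at most 1.4e-13 between no adjustment, quintile main effects, and quintile plus confounder main effects. Standard errors agreed within 0.0001. In one data set the estimate (SE) was 8.519 (3.652) in all three fits and 7.532 (3.930) with quintile × time. In another, generated with a stronger confounder, it was 6.851 (3.656) under every main-effect form. There only the group main effect moved, from 7.63 to about −2. Quintile × time gave 1.971 (4.590).

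**4. Visit 2 scores missing at random (true effect 0, 150 runs each).**

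| Missing | Assumed confounder | Unadjusted | Quintile main effects | Quintile × time |
|---|---|---|---|---|
| 10% | 3 points per SD on change, log-odds 0.6 on group | 1.23 | 1.23 | −0.09 |
| 15% | 8 points per SD on change, log-odds 1.0 on group | 6.21 | 6.16 | 0.20 |

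Simulation error in the first row is about 0.3. In the second row single data sets shifted by 0.35 points on average (at most 1.5), but the bias stayed.

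**5. Size.** From section 6.4: n = 118, 40% outpatient, SD 20. Assumed, because the documents do not give them: correlation 0.5, no true effect, and one measured confounder moving change by 1, 2, 3 or 5 points per SD with exposure log-odds 0.3, 0.6 or 0.9 per SD. That makes 12 scenarios, each run 4,000 times as a change-score regression, which is equivalent to the mixed model with complete data.

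| Scenario | Bias, unadjusted = main effects | False positives |
|---|---|---|
| 1 point, 0.3 | 0.2 | 4.5% |
| 3 points, 0.6 | 1.7 | 7.4% |
| 5 points, 0.9 | 3.8 | 16.1% |

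Across all 12 scenarios, quintile × time gave bias from −0.1 to 0.4 and false positives from 4.5% to 5.1%. Pooled within-quintile differences in change gave the same range of bias.

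**6. Hand check.** At correlation 0.5 the SD of change is 20 and the SE is 20 × 0.188 = 3.76. A bias of 1.7 is 0.45 SE, so the false-positive rate is P(Z > 1.51) + P(Z < −2.41), about 7.4%. A bias of 3.8 is 1.01 SE, which gives about 17%. Both are close to the simulated rates.

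**The case against.** The strongest reply is that 6.3.1 describes subclassification, not covariate adjustment. Patients are grouped by quintile, exposure within each quintile is checked for adequate numbers and balance, and comparability is described within strata. If differences in change are estimated within quintiles and pooled, the adjustment works. The fixed-effects sentence lists no propensity term of any kind, so it does not by itself favour main effects. The sentence "All models will be adjusted for baseline propensity scores by quintiles" follows the models for the patient-centered outcomes survey, which is given only at Visit 2 (section 4.4), and main effects are adequate there.

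This makes the within-quintile reading possible. It does not settle the matter: the plan never says that estimates are made within strata and gives no pooling rule or weights, and its nearest statement on how quintiles are used is ordinary covariate language.

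The reply on size also has force. The confounder strengths are assumed, the weakest scenario is harmless, and 16.1% belongs to the extreme corner of the grid. Sections 1.1 and 3.3.2 describe management as varying by institution, so strong patient-level selection is not established, although hospital-level confounding remains possible. Every bias in the grid is below 6.8 points, the smallest detectable difference in the plan. But a bias smaller than that still raises the error rate, as the 7.4% for 1.7 points shows.

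**Conclusion.** The concern holds. The form of adjustment in the primary model is unspecified, and the form does real work: the ordinary-covariate reading makes the plan's confounding control inert for its primary test. That equality is algebraic for complete pairs and does not depend on any assumed confounder strength. With 10% to 15% of Visit 2 scores missing it is approximate, and the bias persists.

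The size is illustrative only. It ranges from negligible (0.2 points) to material (3.8 points) within the assumed grid, and it concerns only measured factors that affect change. This should be fixed before the analysis. It does not undermine the design, and the within-quintile reading would remove the problem if the plan stated it.

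**What to change.** State in 6.3.1 that propensity quintile and each remaining unbalanced confounder enter the mixed model with both a main effect and an interaction with time, and that the group-by-time coefficient from that model is the primary estimate. The alternative is to state that differences in change are estimated within quintiles and pooled, and to give the weights. Apply the same rule to the financial toxicity total score in 6.3.2.

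ANCOVA on the Visit 2 score should not be used as a substitute, because in a non-randomised cohort it answers a different question. With an unmeasured factor acting equally on both visits (assumed 8 points per SD, log-odds 0.6, 3,000 runs, true effect 0), bias was −0.07 for quintile-adjusted change, 1.83 for ANCOVA and 4.32 for the Visit 2 score alone.

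No new data are needed. The model gains about four quintile × time terms, plus one for each added binary or continuous confounder. In the simulations the standard error was on average 0% to 9% wider, up to 10% with one confounder × time term added, and about 18% to 19% wider at the 95th percentile of single data sets. By normal approximation, where 80% power corresponds to 2.80 standard errors, a 9% increase gives 2.80/1.09 − 1.96 = 0.61, or about 73% power. A 19% increase gives 2.80/1.19 − 1.96 = 0.39, or about 65%. Section 6.4 should acknowledge this loss. If pooling is chosen, cells are sparse: the quintile with fewest outpatients held 3.6 to 6.2 on average.

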6.3.2 Analysis of Secondary Outcomes of Interest

Responses to each of the items on the PIP-D were summed to obtain a total score reflecting the amount of difficulty experienced when handling events faced by parents of children with serious illness. Higher scores indicate greater difficulty and increased pediatric parenting stress (31).

Responses to each of the items on the SDSC DIMS subscale are summed to get a total domain score that is mapped to a corresponding T-score using the SDSC scoring sheet. Higher T-scores are reflective of greater clinical severity of symptoms and a T-score greater than 70 is considered pathological (32). For the PCO, we will utilize appropriate standard statistical methods to evaluate the relationships with neutropenia management strategy

(outpatient versus inpatient). For binary outcomes, log-binomial regression with robust error estimates will be employed to obtain risk ratios (95% CI). For continuous outcomes, generalized linear models will be used incorporating the appropriate distribution based on a graphical assessment of the outcome data. All models will be adjusted for baseline propensity scores by quintiles. Log-binomial regression with robust error estimates will also be employed to obtain risk ratios (95% CI) comparing the incidence of any financial toxicity (versus none), separately for each item on the financial toxicity survey as well as overall across all survey items. For the total score obtained from the financial toxicity survey, we will utilize methods comparable to those described for the PedsQL™ total score in section 6.3.1 above.

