4.2 Screening Visit

The eligibility criteria for participation will be confirmed prior to approaching for consent. Eligible patients interested in the study will be approached for consent at any time from AML/MDS diagnosis through last day of chemotherapy in the treatment course under study. In some cases, the patient's caregivers may not be present in the hospital to provide consent. In these cases, study personnel will obtain verbal consent from the caregivers and child assent (if appropriate).

4.3 Visit 1

Visit 1 will occur prior to the last day of chemotherapy administration in the course. This visit will include:

- 3 baseline health-related quality of life (HRQOL) PedsQL™ survey modules (core, cancer, and fatigue)
- 2 Brief demographic surveys to capture covariates unavailable in the medical record
- 1 Financial toxicity survey

Surveys will be administered via paper or a smart device and will last a total of 15-30 minutes per respondent. In the case that the child is 5 years of age or older, the child self-report and parent proxy-report scales will be separately administered to the child and caregiver, respectively. If the child is between 5 and 8 years of age, Study Personnel will read the survey questions to the patient. There is an illustrated response aid for these young patients. These age-specific PedsQL instruments have been previously validated. The child will indicate their answer as 'Not at all', 'Sometimes', or 'A lot' by pointing to a smiling, middle, or frowning face, respectively. If the child is under 5 years of age, only the parent-proxy version will be administered. Caregivers will also be asked to complete the demographic covariate surveys and the financial toxicity survey during Visit 1. The brief demographic surveys capture covariates unavailable in the medical record, such 'patient race/ethnicity', 'patient/parent education level', and 'parent marital status'. The financial toxicity survey assesses the financial situation of the caregiver/family.

4.4 Visit 2

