5.1.2 Medical Record Abstraction

Medical record abstraction will be performed as per the related Protocol 15-012074 Aim 1: Managing neutropenia in pediatric AML protocol. The table below includes a complete list of the data elements to be abstracted. St. Jude Children's Research Hospital is not participating in Aim 1 and therefore will follow the abstraction process outlined in the Aim 3 Protocol Addendum. The abstracted data elements will be linked to the quality of life and PCO data described in the current protocol.

Variable

Date of birth
Sex
Patient race/ethnicity
Date of AML (or MDS) diagnosis
Age at AML (or MDS) diagnosis
Vital status
Date of death or date of last known follow-up
Location of death (in hospital or at home)
AML subtype
AML risk classification and cytogenetics
Hospital admission start/stop dates
Chemotherapy course number
Chemotherapy regimen and start/stop dates
Course start/stop dates
On COG protocol or similar clinical trial?
Documentation of deviation from planned chemotherapy course
Presence/type of central line
MRD post courses and dates of MRD obtained
Post course remission status
Daily max. fever; how was temperature taken
Infections during chemotherapy courses
ICU care during chemotherapy courses
ANC measurements post chemotherapy
Dates of ANC measurements
Dates and results of microbiological cultures/PCRs onset during post chemotherapy course follow-up
Mucositis severity by course
Systemic antimicrobial prophylaxis at each course
Height, weight, and body surface area at end of chemotherapy course
Nutritional status/supplemental support requirements on day of chemotherapy completion
Ability to practice oral hygiene
Insurance status at course start (private, self-pay, public, other)
English spoken?
Home address
Availability of working telephone
Automobile/taxi voucher requirements
Caregiver's relation to patient
Caregiver's marital status
If caregiver is married, relation between caregiver's spouse and patient
Date of relapse
Site of relapse
Date of transplant
Type of transplant

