5.1.3 Evaluations and Measures

Three evaluation tools will be utilized over the two study visits: 2 demographic covariate surveys, PedsQL™ scales, and a PCO Survey.

- **Demographic covariate survey**

The following patient-level information will be obtained via survey to capture covariates unavailable or less readily available in the medical record:

- Patient race/ethnicity
- Parental employment status
- Household income
- Parental and patient education level
- Number of adults living in the primary residence
- Number of other children living in the primary residence

- Demographic covariate survey II

The following patient-level information will be obtained via survey to capture covariates unavailable or less readily available in the medical record:

- Parent/legal guardian who signed informed consent
- Relation to patient (i.e. mother, father, other)
- Parent/legal guardian marital status

- **PedsQL™**

HRQOL will be assessed using the following validated PedsQL™ scales:

- The 23-item multidimensional 4.0 Generic Core Scales:
 - Physical functioning (8 items)
 - Emotional functioning (5 items)
 - Social functioning (5 items)
 - School functioning (5 items)
- The 18-item multidimensional Fatigue Scale:
 - General fatigue (6 items)
 - Sleep/rest fatigue (6 items)
 - Cognitive fatigue (6 items)
- The 27-item multidimensional 3.0 Cancer Module:
 - Pain/hurt (2 items)
 - Nausea (5 items)
 - Procedural anxiety (3 items)
 - Treatment anxiety (3 items)
 - Worry (3 items)
 - Cognitive problems (5 items)
 - Perceived physical appearance (3 items)
 - Communication (3 items)

- **Financial toxicity survey**

- 11-item survey that assesses the financial situation of the caregiver/family.

Items inquire about:

- Having enough money to cover cost of child's treatment

- Out-of-pocket expenses exceeding their expectations
- Worrying about future financial problems
- Feeling like have no choice about amount spent on care
- Feeling frustrated that cannot work or contribute as much as usual
- Satisfaction with current financial situation
- Ability to meet monthly expenses
- Feeling financially stressed
- Concern about keeping job and income
- Overall control of financial situation

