parent's ability to work and care for other children). All items are rated on a five-point Likert scale from 1 (not at all difficult) to 5 (extremely difficult) (31).

The SDSC DIMS assesses sleep indices such as latency and duration, night awakenings, and reluctance to go to bed. All items are measured on a five-point Likert scale, in which 1=never, 2=occasionally, 3=sometimes, 4=often, and 5=always. The SDSC is reported to have high internal consistency among both healthy ($\alpha=0.79$) and sleep disordered participants ($\alpha=0.71$), as well as high test-retest reliability ($r=0.71$) (32).

- **Financial toxicity survey**

The financial toxicity survey will be completed by the parent at both baseline and follow-up (Visit 1 and Visit 2). The survey includes 11 statements about the financial situation of the caregiver/family in relation to the child's treatment adapted from existing literature (37). A 5-point Likert response scale is used for the parent to indicate the degree to which they agree with each statement (0 = Not at all; 1 = A little bit; 2 = Somewhat; 3 = Quite a bit; 4 = Very much).

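### The binary financial-toxicity analyses are called incidence, but section 6.3.2 names no outcome visit and does not say how the Visit 1 response to the same item is used

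*Combined protocol and SAP*

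**What the plan says.** Section 5.1.3 gives the timing: "The financial toxicity survey will be completed by the parent at both baseline and follow-up (Visit 1 and Visit 2"). Section 4.3 places the first of these before the group is known: "Visit 1 will occur prior to the last day of chemotherapy administration in the course". Under section 3.4 the group depends on whether discharge falls within 3 days after chemotherapy ends. Each of the 11 items therefore has an answer that precedes the exposure in the course under study.

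Section 6.3.2 treats two forms of this outcome differently. The total score borrows the section 6.3.1 mixed model, which uses both visits. The binary form is a log-binomial model "comparing the incidence of any financial toxicity (versus none), separately for each item" and overall across items. No outcome visit, at-risk set or baseline term is named for it.

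The stated adjustment is general: "All models will be adjusted for baseline propensity scores by quintiles". Section 6.3.1 builds that score "conditional on all baseline factors determined to be true confounders (i.e., those associated with both exposure and outcome"), and also from factors associated with the outcome only. The Visit 1 financial response is neither named nor excluded. Economic candidates are collected, among them "Household income" in the demographic survey and, in section 5.1.2, "Insurance status at course start (private, self-pay, public, other").

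**The concern.** Incidence means new occurrence. It needs either a set of families free of the item at Visit 1 or, at the least, a model that conditions on the Visit 1 answer. The text commits to neither. Read literally, one analyst could compare any versus none at Visit 2 in all families, another could restrict to families with none at Visit 1, and a third could adjust. These are three different quantities, and the data could favour any of them.

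Household finances can plausibly influence both early discharge and later hardship. If the Visit 2 comparison is run in all families and the propensity score does not capture Visit 1 hardship, a difference that existed before discharge is reported as a risk ratio for management strategy. If the groups are balanced, families already in hardship still sit in both numerators. That pulls the ratio toward 1 relative to an incidence ratio and leaves out a strong predictor. Up to 12 risk ratios (11 items plus overall) are affected, and section 9 plans to share the results with families.

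**Working it through.** **The plan's own figure.** None is given for the binary financial analyses. The only power statement (section 6.4) concerns the PedsQL total score, and it reproduces. At correlation 0 the SD of change is 20√2 = 28.28, the SE is 28.28 × √(1/47 + 1/71) = 5.32, and a 15.0-point difference has power 0.80. At correlation 0.8 a 6.8-point difference has power 0.81. This does not bear on the present point except to supply the group sizes, 47 outpatient and 71 inpatient.

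**Step 1: what a Visit 2-only ratio estimates.** Let b be prevalence at Visit 1, q the probability that hardship persists, and i the new-onset risk. Visit 2 prevalence in a group is b·q + (1 − b)·i. All values of b, q and i below are assumed.

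*Imbalanced at Visit 1, no true effect (i = 0.20 in both groups), no adjustment:*
- 40% outpatient vs 60% inpatient, q = 1: (0.40 + 0.60 × 0.20)/(0.60 + 0.40 × 0.20) = 0.52/0.68 = 0.765.
- The same with q = 0.8: 0.44/0.56 = 0.786.
- 60% vs 40%: 0.68/0.52 = 1.308 (q = 1) or 0.56/0.44 = 1.273 (q = 0.8).
- At 47 vs 71 a test rejects about 40–42% of the time for q = 1 and about 25% for q = 0.8. A 20-point imbalance is large, so this shows direction and mechanism more than likely size.

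*Balanced at Visit 1, true new-onset ratio 0.10/0.20 = 0.50, q = 1:*
- b = 20%: 0.28/0.36 = 0.778. Families at risk: 47 × 0.8 ≈ 38 and 71 × 0.8 ≈ 57.
- b = 50%: 0.55/0.60 = 0.917. At risk: about 24 and 36.
- b = 80%: 0.82/0.84 = 0.976. At risk: about 9 and 14.

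Imbalance therefore creates a false effect, and balance dilutes a real incidence ratio. Restriction recovers 1.00 or 0.50 but may leave few families.

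**Step 2: how far the stated adjustment helps.** Simulated data, with assumptions as follows: latent normal hardship cut at prevalence 40% or 60%; correlation 0.7 or 0.9 between visits; a 0.35 SD shift at Visit 1; no effect of management; risk ratio from Poisson regression with robust variance.

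| Adjustment | False positives | Risk ratio (true 1.00) |
|---|---|---|
| None | about 17–29% | about 1.15–1.32 |
| Quintiles from a moderate proxy of Visit 1 hardship | about 13–21% | about 1.11–1.24 (proxy correlation 0.5) |
| Quintiles from the Visit 1 total score | about 7–11% | not tabulated |
| Visit 1 item added | about 4–8% | about 1.03–1.07 |

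With 800 datasets per setting, the Monte Carlo standard error is √(0.05 × 0.95/800) = 0.8 points near 5% and √(0.20 × 0.80/800) = 1.4 points near 20%. The last row is close to nominal. The total-score row is the most sensitive to assumption, because it depends on how far the 11 items share the imbalance.

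**Step 3: balanced baselines.** Relative to proxy-based quintiles, adding the Visit 1 item cuts the standard error by about 8–22%. With an assumed true effect, power rises from 35–36% to 41–42% at correlation 0.7 and from 33–38% to 54–62% at correlation 0.9.

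**Step 4: the overall outcome.** If the 11 items were independent with prevalence p each, the chance of at least one is 1 − (1 − p)^11: 69% for p = 0.1, 91% for 0.2, 98% for 0.3. Correlated items give lower figures, but Visit 1 any/none across items may still be nearly constant and adjust for little.

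**The case against.** A reader might infer that the plan ignores Visit 1, that earlier hardship will therefore be counted as an effect of management, and that 17–29% is the planned analysis's error rate. The documents do not support this, for three reasons.

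First, section 6.3.2 is silent on the outcome visit. Incidence could there mean new toxicity among families with none at Visit 1. The accurate statement is that the plan does not say it uses the Visit 1 response.

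Second, the section 6.3.1 screening rule tests each baseline covariate against each outcome and keeps those related to the outcome. A strong predictor measured at Visit 1 is what such a rule would tend to select, and income, employment, education and insurance are also candidates. If the score carries the item's own Visit 1 response on its 0–4 scale, simulated false positives fall to about 5%, with risk ratios of 1.02–1.03. The 17–29% range comes from a model with no propensity score, which is not what is planned.

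Third, reach is limited. Section 6.1 lists financial toxicity scores as the secondary outcome, and the total score is already modelled with both visits.

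All three stand. What they do not remove is the lack of commitment. Data-driven screening may or may not select Visit 1 hardship. One quintile score cannot condition closely on 11 separate item baselines. The further step of controlling confounders that remain unbalanced is written in section 6.3.1 and carried over only to the financial total score.

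**Conclusion.** The concern holds as a gap in specification with a plausible statistical cost. The label and the stated model do not match, and a Visit 2-only ratio would be a prevalence ratio. Bias arises only if Visit 1 hardship remains imbalanced after propensity adjustment. With balance, the cost is lost precision and a ratio closer to 1 than the incidence ratio (a true 0.50 appearing as 0.78–0.98 in the illustration).

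Under the simulated conditions, the excess of false positives ranges from close to nothing, if the score carries the item's own Visit 1 answer, to about 13–21% if it carries only a moderate proxy. Prevalence, correlation, persistence and the 0.35 SD imbalance are all assumed, since the documents give none, so no single figure can be called the plan's error rate. The point affects supplementary binary contrasts of a secondary outcome and leaves the primary analysis untouched. It is worth correcting because the needed answers are already collected.

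**What to change.** In section 6.3.2:
- Name Visit 2 as the outcome visit for the binary financial models, and write down what counts as any toxicity on the 0–4 scale, including for positively worded items.
- Add the same item's Visit 1 response as a covariate, alongside the propensity quintiles, in each item model. For the overall outcome use the Visit 1 total score, for the reason in step 4.
- Call the estimate a baseline-adjusted risk ratio at Visit 2. Adjustment deals with imbalance and precision, but it does not turn the estimate into an incidence ratio.
- Report new onset among families with none at Visit 1 descriptively, because few may be at risk.
- State that the estimate concerns the course under study. Consent is allowed in any frontline course, so Visit 1 answers may already reflect how earlier courses were managed.

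The cost is a few sentences and one covariate per model, with no new data or visits; all dyads with both surveys are kept. The extra term may cause log-binomial models not to converge. Poisson regression with robust variance can be named in advance as the fallback.
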